To evaluate the IRRC-assessed objective response rate (ORR) of nivolumab monotherapy and nivolumab in combination with either ipilimumab or anti-LAG-3 antibody (BMS-986016) in dMMR/MSI-H mCRC; the ORR of nivolumab combined with ipilimumab in subjects with metastatic non-MSI-H (pMMR) CRC; and, the IRRC ORR of nivolumab combined with daratumumab therapy in subjects with metastatic non-MSI-H (pMMR) mCRC.

To evaluate the disease control rate (DCR) of nivolumab monotherapy or combined with the above agents in subjects with metastatic mCRC.

[figure not shown]
Exploratory Objectives

Listed in protocol Section 1.3.3.

[figure not shown]
Study Design: CA209142 is a Phase 2 open-label, multi-center trial of nivolumab monotherapy (Cohort N) or in combination therapy (Cohort N + I) to estimate the response rate in MSI-H CRC and non-MSI-H CRC. CA209142 completed a safety cohort of subjects with non-MSI-H CRC to assess the safety and tolerability of nivolumab in combination with ipilimumab in subjects with non-MSI-H CRC in preparation for an analogous 2-stage assessment of the response rate for the combination in MSI-H CRC.

As described in **Figure 1**, subjects with recurrent or metastatic CRC received nivolumab or nivolumab with ipilimumab, depending on the response rate in the monotherapy MSI-H cohort and tolerability of the nivolumab combined with ipilimumab combination in the non-MSI safety cohort.

Figure 1: Study Design Schematic

FOLLOW-UP MIN. 12 WEEKS. FOLLOW-UP FOR SURVIVAL MIN. OF 5 YEARS.

mStage = monotherapy Stage; cStage = combination Stage; Arm N = Nivolumab monotherapy; Arm N+I = nivolumab in combination with ipilimumab; nMSI-H N+I = non-MSI-H nivolumab in combination with ipilimumab

Two Stage Design: Both Arms N and N+I will follow a two-stage design to test whether nivolumab monotherapy or nivolumab combined with ipilimumab yields an objective response rate (ORR) that is of clinical interest in MSI-H metastatic colorectal cancer mCRC. On treatment stages that meet an ORR threshold will proceed from Stage 1 to Stage 2 (same for both m and cStage). **Table 1** contains the efficacy criteria decisions.

Table 1: Efficacy Criteria to Proceed from Stage 1 to Stage 2

mStage 1 Efficacy Criteria	Next Step
≥ 7/19 subjects have confirmed CR or PR	Go into mStage 2
3-6/19 subjects have confirmed CR or PR	Close mStage 1 & open cStage 1
≤ 2/19 subjects have confirmed CR or PR	Close Trial
cStage 1 Efficacy Criteria	

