- 5. Subjects with a condition requiring systemic treatment with either corticosteroids (> 10 mg daily prednisone equivalents) or other immunosuppressive medications within 14 days of study drug administration. Inhaled or topical steroids and adrenal replacement doses > 10 mg daily prednisone equivalents are permitted in the absence of active autoimmune disease.

Re-initiation of Treatment for MSI-H Cohorts

Subjects in MSI-H cohorts who discontinue study treatment at Maximal Clinical Benefit, (Section 3.1.4.1) are permitted to re-initiate treatment, if disease progression defined by RECIST criteria occurs within 1 year (≤52 weeks) and protocol-defined criteria (Section 4.3.9) are met.

Study Assessments: The primary endpoint of this study is ORR which is based on tumor assessments at baseline and then at 6 weeks from first dose which continue every 6 weeks for the first 24 weeks and every 12 weeks thereafter until disease progression (investigator-assessed RECIST 1.1-defined progression) or treatment discontinuation, whichever occurs later.

Statistical Considerations:

Sample Size: This study will consist of 5 cohorts: non-MSI-H safety cohort, MSI-H cohort (Cohort N and Cohort N+I), Cohort C3 (MSI-H subjects who have not had prior therapy for their metastatic disease), MSI-H Cohort C5 Cohort and non-MSI-H Cohort C6. It is expected to treat up to approximately 96 central-pathology-lab-confirmed subjects (up to 29 non-MSI-H and up to 67 MSI-H) for the initial non-MSI-H and MSI-H cohorts. It is expected to treat approximately 30 subjects in cohort C3. It is expected to treat approximately 40 MSI-H subjects in C5 Cohort and 40 non-MSI-H subjects C6 Cohort.

Sample size determination for non-MSI-H and MSI-H cohorts:

The MSI-H cohort will include subjects who are defined as MSI-H based on standard diagnostic testing documented in the subject's medical history and prospectively confirmed in the current study by repeat testing using a polymerase chain reaction (PCR) test.

The non-MSI-H safety cohort will include all subjects testing non-MSI-H by the repeat PCR test, including those who were MSI-H by medical history but not confirmed by repeat testing.

For the non-MSI-H safety cohort, sample size is not based on power considerations and will depend on the observed toxicity.

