For the MSI-H cohort, a Simon optimal two-stage design will be used to test the null hypothesis that the true ORR is $\leq 30\%$ (not considered clinically compelling) with either nivolumab monotherapy or the combination of nivolumab/ipilimumab. In the first stage (mStage 1), 19 subjects will be treated with nivolumab monotherapy. If there are 2 or fewer responses in these first 19 treated subjects, the protocol will be closed to further enrollment. If there are more than 2 but less than 7 responses in the first 19 treated subjects, accrual to the monotherapy arm will be stopped, and the combination arm will be opened for accrual. Otherwise, if there are 7 or more responses in the first 19 treated subjects, approximately 29 additional subjects will be accrued to the monotherapy arm (mStage 2) to target a total of 48 treated subjects.

If accrual to the combination arm is opened to the MSI-H cohort as specified above, stage I of the Simon two-stage design will be initiated in the combination arm with 19 treated subjects (cStage 1). If there are 6 or fewer responses in these first 19 treated subjects, accrual to the combination arm will be stopped. Otherwise, approximately 29 additional subjects will be accrued to the combination arm (cStage 2) to target a total of 48 subjects treated with combination therapy.

Subjects whose repeat testing does not confirm MSI-H status will be replaced in order to obtain the required number of subjects in each stage of the Simon design. Note that because of the delay in obtaining the centrally evaluated MSI status, more than 48 subjects may be treated with monotherapy and combination therapy in these initial cohorts.

The null hypothesis will be rejected if 20 or more responses are observed in 48 treated subjects in the remaining open arm (nivolumab monotherapy or nivolumab/ipilimumab combination).

Within a given treatment arm, this design yields a one-sided type I error rate of 5% and power of 90% when the true response rate is 52%

Sample size determination for Cohort C3:

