3 INVESTIGATIONAL PLAN

3.1 Study Design and Duration

[figure not shown]
CA209142 is a Phase 2 open-label, multi-center, trial of nivolumab monotherapy (Arm N) or in combination therapy (Cohort N + I) to estimate the response rate in MSI-H CRC and non-MSI-H CRC. CA209142 completed a safety cohort of subjects with non-MSI-H CRC to assess the safety and tolerability of nivolumab in combination with ipilimumab in subjects with non-MSI-H CRC in preparation for an analogous 2-stage assessment of the response rate for the combination in MSI-H CRC.

As described in Figure 3.1-1, subjects with recurrent or metastatic CRC received nivolumab or nivolumab with ipilimumab, depending on the response rate in the monotherapy MSI-H cohort and the tolerability of the nivolumab combined with ipilimumab combination in the non-MSI safety cohort.

[figure not shown]
Protocol Amendment No: 09 Date: 27-Aug-2021

Approved v1000 930073805 10.0

Figure 3.1-1: Study Design Schematic (Arm N and Arm N +I) and Non-MSI-H Safety Cohort

FOLLOW-UP MIN. 12 WEEKS. FOLLOW-UP FOR SURVIVAL MIN. OF 5 YEARS.

mStage = monotherapy Stage; cStage = combination Stage; Arm N = Nivolumab monotherapy; Arm N+I = nivolumab in combination with ipilimumab; nMSI-H N+I = non-MSI-H nivolumab in combination with ipilimumab

For the monotherapy mStage 1, if 7 or more subjects with microsatellite metastatic CRC (MSI-H mCRC) have a confirmed PR or CR, mStage 2 will open to enroll an additional 29 subjects. A confirmed PR or CR is defined as a subsequent confirmatory scan performed ≥ 4 weeks after the first scan. If there are more than 2 but less than 7 responses in the first 19 subjects, accrual to the mStage1 arm will be stopped, and the combination cStage1 arm will be opened for accrual.

CA209142 will also contain a safety cohort of subjects with non-MSI-H mCRC to assess the safety and tolerability of nivolumab in combination with ipilimumab in subjects with non-MSI-H mCRC and provide the starting dose for cStage 1.

[figure not shown]
If 7 or more subjects in cStage 1 with MSI-H mCRC have a confirmed PR or CR, cStage 2 will open to enroll an additional 29 subjects. If 6 or fewer of the first 19 subjects with MSI-H mCRC have a confirmed PR or CR, cStage 1 will close, and the trial will end. Additionally, if 2 or fewer of the first 19 subjects in mStage 1 have a confirmed CR or PR, the trial will close. The determination of response rate will be based on investigator-assessed tumor response per RECIST

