3.1.2 Non-MSI-H Subjects (Independent Safety Sub-Trial)

An independent safety sub-trial in non-MSI H subjects will inform the safe and tolerable dose level for cStage 1 in subjects with MSI-H mCRC. The combination of nivolumab and ipilimumab is already being evaluated in Phase 3 in advanced melanoma and has more recently been tested in NSCLC and RCC. This regimen is expected to also be tolerable in mCRC, but given the potential for gastrointestinal toxicities with ipilimumab and nivolumab (eg, colitis), a dose escalating safety phase will assess the safety and tolerability of nivolumab in combination with ipilimumab and evaluate different doses of each agent. Enrollment in the non-MSI-H N+I Safety Sub Trial will occur in parallel to mStage 1.

3.1.2.1 Dose Escalating Safety Evaluation for Nivolumab in Combination with Ipilimumab in non-MSI- H Subjects

Table 3.1.2.1-1 contains the dose levels for the non-MSI-H dose escalation safety cohort.

Table 3.1.2.1-1: Dose Cohort for Safety non-MSI-H N+I			
Dose Cohort Level	Nivolumab (mg/kg)	Ipilimumab (mg/kg)	
-1	0.3	1	
1	1	1	
2a	1	3	
2b	3	1	

The first dose cohort will be Dose Level 1, 1 mg/kg each of nivolumab and ipilimumab. If this combination is deemed tolerable, then subjects will be randomized (1:1) to one of two dose levels:

- Dose Level 2a (N1+I3): 1 mg/kg nivolumab + 3 mg/kg ipilimumab, or
- Dose Level 2b (N3 + I1): 3 mg/kg nivolumab + 1 mg/kg ipilimumab

The tolerable dose of the combination will be brought into an analogous 2-stage design if nivolumab monotherapy (mStage 1) does not have 7 or more responders out of the first 19 subjects.

If Level 1 is not tolerable, then Level -1 will be initiated. There will be no dose escalation beyond Levels 2a and 2b. Once the decision on the dose level for further investigation has been confirmed, that dosing level will be used in cStage 1 in subjects with MSI-H (Section 3.1.4.3).

Subjects need to be followed up for at least 6 weeks after start of study treatment before determination of the tolerability of a dose level. However, tolerability beyond 6 weeks may also be taken into consideration.

The criteria for tolerability for Dose Level 1 (and -1 if necessary) (Table 3.1.2.1-2) are based on drug-related adverse events leading to permanent discontinuation (listed in Section 4.3.6) and include:

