8 STATISTICAL CONSIDERATIONS

8.1 Sample Size Determination

This study will consist of 5 cohorts: non-MSI-H safety cohort, MSI-H cohort (Cohort N and Cohort N+I), Cohort C3 (MSI-H subjects who have not had prior therapy for their metastatic disease), Cohort MSI-H C5, and Cohort non-MSI-H C6. All information pertaining to the C4 cohort was added via a site-specific Amendment 06. It is expected to treat up to approximately 96 subjects (up to 29 non-MSI-H and up to 67 MSI-H) for the initial non-MSI-H and MSI-H cohorts. It is expected to treat approximately 30 subjects in cohort C3. It is expected to treat approximately 40 MSI-H subjects in C5 Cohort and 40 non-MSI-H subjects C6 Cohort.

Sample size determination for the non-MSI-H safety Cohort and MSI-H Cohort:

The MSI-H cohort will include subjects who are defined as MSI-H based on standard diagnostic testing documented in the subject's medical history and prospectively confirmed in the current study by repeat testing using a PCR test.

The non-MSI-H cohort will include all subjects testing non-MSI-H by the repeat PCR test, including those who were MSI-H by medical history but not confirmed by repeat testing.

For the non-MSI-H safety cohort, sample size is not based on power considerations and will depend on the observed toxicity.

For the MSI-H cohort, a Simon optimal two-stage design will be used to test the null hypothesis that the true ORR is $\leq 30\%$ (not considered clinically compelling) with either nivolumab monotherapy or the combination of nivolumab/ipilimumab. In the first stage (mStage 1), 19 subjects will be treated with nivolumab monotherapy. If there are 2 or fewer responses in these first 19 treated subjects, the protocol will be closed to further enrollment. If there are more than 2 but less than 7 responses in the first 19 treated subjects, accrual to the monotherapy arm will be stopped, and the combination arm will be opened for accrual. Otherwise, if there are 7 or more responses in the first 19 treated subjects, approximately 29 additional subjects will be accrued to the monotherapy arm (mStage 2) to target a total of 48 treated subjects.

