If accrual to the combination arm is opened to the MSI-H cohort as specified above, stage I of the Simon two-stage design will be initiated in the combination arm with 19 treated subjects (cStage 1). If there are 6 or fewer responses in these first 19 treated subjects, accrual to the combination arm will be stopped. Otherwise, approximately 29 additional subjects will be accrued to the combination arm (cStage 2) to target a total of 48 subjects treated with combination therapy.

Subjects whose repeat testing does not confirm MSI-H status will be replaced in order to obtain the required number of subjects in each stage of the Simon design. Note that because of the delay in obtaining the centrally evaluated MSI status, more than 48 subjects may be treated with monotherapy and combination therapy in these initial cohorts.

The null hypothesis will be rejected if 20 or more responses are observed in 48 treated subjects in the open arm (nivolumab monotherapy and/or nivolumab/ipilimumab combination). Within a

given treatment arm, this design yields a one-sided type I error rate of 5% and power of 90% when the true response rate is 52%.

Sample size determination for Cohort C3:

The sample size determination for Cohort C3 was not based on power consideration but to provide precision on estimation of ORR. Saltz and coworkers reported ORR of 49% and 38% in chemotherapy group, per investigator assessment and per independent response review committee assessment, respectively, in this patient population. Table 8.1-1 presents the 95% CI for ORR ranging from 45% to 65%, which are considered meaningful clinical outcome, with a sample size of 30 subjects.

Table 8.1-1: Interval Estimation and Coverage Probability -Clopper-Pearson Method (95% Confidence Interval)

Sample size	Number of responses	Response rate	Confidence interval
30	13	0.43333	(0.2546, 0.6257)
30	14	0.46667	(0.2834, 0.6567)
30	15	0.50000	(0.3130, 0.6870)
30	16	0.53333	(0.3433, 0.7166)
30	17	0.56667	(0.3743, 0.7454)
30	18	0.60000	(0.4060, 0.7734)
30	19	0.63333	(0.4386, 0.8007)
30	20	0.66667	(0.4719, 0.8271)

Sample size determination for Cohort C5:

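### Does *and/or* in the Section 8.1 rejection rule, against *or* in the synopsis, change which arm is tested at 48 subjects?

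*Combined protocol and SAP*

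**What the plan says.** Section 8.1 (Sample Size Determination) states the rejection rule as "20 or more responses are observed in 48 treated subjects in the open arm (nivolumab monotherapy and/or nivolumab/ipilimumab combination". The sample size text of the synopsis gives the same threshold "in the remaining open arm (nivolumab monotherapy or nivolumab/ipilimumab combination". Two things differ: the synopsis has the word *remaining*, and it has *or* where 8.1 has *and/or*.

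The gate that decides which arm goes on is stated in several places:

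- Synopsis, Table 1, for 3 to 6 responses in 19: "Close mStage 1 & open cStage 1".
- Section 3.1, for the same range: "accrual to the mStage1 arm will be stopped, and the combination cStage1 arm will be opened for accrual".
- Section 3.1.2.1: the combination enters its own two-stage design "if nivolumab monotherapy (mStage 1) does not have 7 or more responders out of the first 19 subjects".
- Section 8.1: "If there are more than 2 but less than 7 responses in the first 19 treated subjects, accrual to the monotherapy arm will be stopped", after which the combination arm opens.

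With 7 or more responses, monotherapy continues to 48 and no opening of the combination arm is described. With 2 or fewer, enrolment closes.

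On numbers, 8.1 says "It is expected to treat up to approximately 96 subjects (up to 29 non-MSI-H and up to 67 MSI-H" in the initial cohorts. The synopsis gives the same total but describes it as "approximately 96 central-pathology-lab-confirmed subjects".

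**The concern.** The sentence is the decision rule for the primary endpoint in Arms N and N+I, so a reader should get the same answer from the synopsis and from Section 8. Taken literally, *and/or* allows for both arms to be tested at 48. The gate and the expected maximum of 67 MSI-H subjects both rule that out. If two full arms were really intended, the expected maximum would be too low, the rule for opening the combination arm would be missing, and two hypotheses could be tested at full size where the synopsis foresees one. A lesser worry is that 8.1 omits the limit to centrally confirmed subjects that the synopsis puts on the same total.

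**Working it through.** **Inputs.** From 8.1: stage 1 of 19 and stage 2 of 29 per arm, continue at 7 or more, reject at 20 or more of 48, null rate 30%, alternative 52%, one-sided 5%, power 90%, at most 29 non-MSI-H and 67 MSI-H subjects. The gate is as set out above.

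**Paths through the gate** (confirmed MSI-H subjects, before any overrun from replacement):

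| Monotherapy, of first 19 | Combination, of first 19 | Arm N | Arm N+I | Total | Arm tested at 48 |
|---|---|---|---|---|---|
| 2 or fewer | not opened | 19 | 0 | 19 | none |
| 3 to 6 | 6 or fewer | 19 | 19 | 38 | none |
| 7 or more | not opened | 48 | 0 | 48 | N |
| 3 to 6 | 7 or more | 19 | 48 | 67 | N+I |

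The largest total is 19 + 48 = 67, and 29 + 67 = 96. Both reproduce the stated figures. No row has two arms at 48.

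**Per-arm error rates.** With x responses in stage 1,

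P(reject | p) = sum over x = 7 to 19 of C(19, x) p^x (1 − p)^(19 − x) × P(Bin(29, p) ≥ max(0, 20 − x)).

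- p = 0.30: 0.0485, within the stated 5%.
- p = 0.52: 0.9036, matching the stated 90%.

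A grid search over two-stage designs with these limits returns the same design (stop at 6 of 19 or fewer, reject at 20 of 48 or more) as Simon optimal. Its expected size at 30% is 19 + 29 × 0.3345 = 28.7. None of this depends on *or* versus *and/or*.

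**The two sentences, state by state.** In the first two rows no arm reaches 48, so neither sentence is applied. In the third, both apply the 20 of 48 threshold to monotherapy. In the fourth, both apply it to the combination. The verdicts agree throughout.

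**Context in 8.1.** The paragraph on the combination arm is conditional: it applies only if that arm has been opened under the gate just described. The rejection sentence speaks of a single open arm, and the next sentence gives the error rates within one treatment arm. Read in place, it is a per-arm rule.

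**The confirmed-subjects limit.** Directly after the totals, 8.1 defines the MSI-H cohort as positive on medical history and confirmed by repeat PCR. It then says that unconfirmed subjects are replaced and that more than 48 may be treated as a result. Section 8.5 also counts confirmed subjects at the interim. The missing qualifier is supplied by the text around it.

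**The case for a change.** The strongest case is that *and/or* is deliberate. The synopsis says that both arms follow a two-stage design with the same stage 1 threshold, and that starting the combination depends on safety as well as on response. The dosing tables in Section 4.3, the re-initiation table in 4.3.1 and the assignment text in 4.2 treat mStage 1/2 and cStage 1/2 alike as cohorts with treated subjects. If both arms could run to stage 2, the confirmed MSI-H maximum would be 48 + 48 = 96, and the initial cohorts 29 + 96 = 125 with the 29 held fixed. The chance of at least one false rejection when both arms are truly at 30% would also move. Under the gate it is 0.0485 + 0.6193 × 0.0485 = 0.078, where 0.6193 is the chance of 3 to 6 responses in 19. With two independent full arms it is 1 − (1 − 0.0485)² = 0.095.

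Part of this stands. The wording does differ, and the documents cannot show whether both arms went on to stage 2. The rest does not carry. Applying a two-stage design to each arm does not mean that both reach stage 2. A safety condition adds a hurdle to opening the combination and does not open it after 7 or more responses. The stage labels may be no more than arm names. The plan claims 5% within an arm and not across arms, so 0.078 and 0.095 contradict nothing in it. Even if both arms had run, an analyst would apply 20 of 48 to each arm separately, which the 8.1 wording already covers.

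**Conclusion.** The mismatch is a clerical slip with no effect on any result. Under the written gate at most one arm reaches 48, the expected maximum of 67 is right, and both sentences give the same decision in all four reachable states. The per-arm type I error of 4.85% and power of 90.4% hold under either wording. The omitted reference to central confirmation is covered by the adjacent definition and the replacement caveat. Aligning the sentences would be tidier but would alter no threshold, sample size or analysis.

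This rests on the gate as written. Should the sponsor's records show that both arms were allowed into stage 2, the opening rule and the expected totals would be what needs explaining. The rejection threshold would still apply arm by arm.

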8.2 Populations for Analyses

- The following definitions will apply to all cohorts except where otherwise specified:
- The MSI-H cohort will include subjects who are defined as MSI-H based on standard diagnostic testing documented in the subject's medical history (MSI-H per local testing) including those prospectively confirmed in the current study by repeat testing using a PCR test. Subjects in this cohort will be referred to as 'confirmed MSI-H subjects.' Similarly, the non-MSI-H cohort will include all subjects testing non-MSI-H by the repeat PCR test or standard diagnostic testing documented in the subject's medical history.
- All Treated Subjects: All subjects who received at least one dose of study medication within a cohort. This is the primary population for safety and efficacy analysis in any cohort.
- All response evaluable subjects: All treated subjects within a given cohort who have baseline and at least one on-study evaluable tumor measurement.
- PK subjects: All subjects with available serum time-concentration data from subjects dosed with study drug.
- Immunogenicity subjects: all treated subjects with available immunogenicity data.

• PD-L1 measurable subjects: all treated subjects with a measurable PD-L1 expression result.

- Biomarker subjects: All treated subjects with available biomarker data.
- Outcomes Research Subjects: all treated subjects who have an assessment at baseline (Visit 1 assessment prior to administration of drug) and at least 1 subsequent assessment (for EORTC QLQ-C30 and EQ-5D separately).
- All Re-initiation Treated Subjects: All subjects who received at least one dose of study medication following re-initiation of treatment.

